Risks and solutions envisaged for task 2.6: Risk: data loss. Contingency: In order to ensure no data loss, a periodical back up will be carried out.

WP3.- Probiotic effects on AD dementia

The objective of this WP is to enhance the knowledge of the potential positive probiotic effects in the gut composition and on their clinical symptoms of the Alzheimer disease patients. In this sense our group has already done studies of the beneficial effects of the PNU-282987, an alpha 7 nicotinic receptor agonist in an animal model of Alzheimer's disease, with positive results in anxiety symptoms but not in cognitive (Vicens et al, 2013a, 2013b, 2017).

It is generally agreed that probiotic strains should be of host origin with a beneficial effect on the host, withstand into food stuff with a high count of them, withstand transits through intestine and colonize lumen of the tract, produce antimicrobial agents, and be technologically appropriate for industrial production (Shewale et al., 2014). Due to the lack of evidence about the appropriate dosage of probiotics for AD, we used the below-mentioned doses based on few previous studies in healthy subjects (Benton et al., 2007; Mohammadi et al., 2015) and on AD patients with positive results (Akbari et al 2016).

To achieve this objective, the following tasks will be carried out in this WP:

Task 3.1. Patients recruitment and assignment to experimental groups

We will recruit a total of 60 AD patients, 30 will ingest the probiotic mixture and 30 will ingest placebo (randomized assignment to the groups will be done). The experimental group will take the probiotic ingest daily: *Lactobacillus acidophilus*, *Lactobacillus casei*, *Bifidobacterium bifidum*, and *Lactobacillus fermentum* (2×10^9 CFU/g of each). This mixture of bacteria has been showed to have positive results with 12 weeks treatment (Akbari et al, 2016). The duration of the treatment will be 24 weeks, with two posttreatment assessment, at 12 weeks and at 24 weeks.

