To calculate sample size, we used the standard formula suggested for clinical trials by considering type one error(a) of 0.05 and type two error(b) of 0.20 (power = 80%) based on a previous study (Akbari et al, 2016). We used 1.3 as SD and 1.1 as the difference in mean (d) of MMSE as key variable. Accordingly, we needed 25 persons in each group. Assuming 5 dropouts in each group, the final sample size was determined to be 30 persons per group. This sample size is enough to detect differences in cognitive performance due to a probiotic treatment (Akbari et al, 2016).

The criteria for the recruitment will be: Inclusion criteria: AD diagnosed by the neurology service; more than 65 years. Exclusion criteria: Comorbidity with other significant neurology disease, infectious treatment with antibiotics in the previous 6 months prior to providing the stool sample, corticosteroid use, immunosuppressors or immunostimulants treatment, illnesses of the GI tract, large doses of commercial probiotics consumed (greater than or equal to 10^8 cfu per organisms per day).

The hospitals will have publicity of the study and when target patients were attended by the neurologists/neuropsychologist (group research members) will be informed of the study and encourage enrolling. Also, neuropsychologists of the Alzheimer's Association will inform of the study and encourage enrolling. In the Alzheimer stimulation center of Alzheimer Association come regularly about 60-70 patients. If the patients agree to enroll the study, they (or legal tutor) will sign the informed consent and give their contact telephone number to be able to be contacted again. The neurologists/neuropsychologist also will give them the stool collection pack, to be kept for them until the contact of the research team for the interview.

Risks and solutions envisaged for task 3.1: Risk: patient lost from the recruitment until the interview, fail in neuropsychological assessment, fecal collection or treatment adherence. Contingency: we will recruit some more patients of each group 5-10 patients.

Task 3.2. Citation of the volunteers before the probiotic intake period: assessment, stool sample collection and treatment initiation

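### WP3 admits AD of any severity, ignores severity in the assignment and compares arms with an unadjusted t-test, although it plans on an MMSE SD of only 1.3

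*Combined protocol and SAP*

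**What the plan says.** Task 3.1 (WP3) gives the inclusion criteria as "AD diagnosed by the neurology service; more than 65 years". The exclusions cover other neurological disease, antibiotics, corticosteroids, immune treatments, gastrointestinal illness and high-dose probiotics. None sets a limit on MMSE, CDR or GDS-FAST.

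On allocation, the same section gives 30 patients per arm and says only that "randomized assignment to the groups will be done". On sample size it says "We used 1.3 as SD and 1.1 as the difference in mean (d) of MMSE as key variable", and then "Accordingly, we needed 25 persons in each group". Five dropouts per arm bring this to 30.

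Task 3.2 lists MMSE, GDS-FAST and CDR among the assessments at the visit where the product is first handed out, and the entry criteria are reviewed at that visit. Task 3.6 names Student's t-test and the chi-square test for comparing the groups. It names no baseline covariate and does not say whether the t-test is applied to scores or to changes from baseline.

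**The concern.** MMSE is the variable on which the trial is sized, and it is also a measure of disease severity. With no limit on severity, MMSE scores may vary widely between patients at entry. The planning SD of 1.3 would place about 95% of values in a band of roughly 5 points (2 × 1.96 × 1.3 = 5.1), which is narrow for scores from an AD sample with no severity limit.

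Two features would normally control this spread: using severity in the assignment, and using baseline MMSE in the analysis. The plan has neither. If the t-test is run on scores, between-patient spread goes straight into the standard error. A chance difference in severity between the arms could then match the effect sought, leaving a result that is hard to interpret in either direction.

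**Working it through.** **Inputs from Task 3.1.** Difference 1.1, SD 1.3, alpha 0.05, power 80%, 25 per arm before dropout, 30 per arm randomised. Sidedness is not stated; two-sided is assumed.

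**The plan's own figure.** n per arm = 2 × 1.3² × (1.960 + 0.842)² / 1.1² = 21.9, so 22. The exact t calculation gives 23. The stated 25 is slightly conservative, with power 83% by the t calculation. The sample size therefore stands if an SD of 1.3 is right for the quantity analysed.

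**Chance baseline difference and power by SD.** The documents give no baseline MMSE SD, so every value except 1.3 is an assumption. The standard error of the baseline difference is SD × √(2/30) = 0.258 × SD. The chance that the arms differ by more than 1.1 is 2 × [1 − Φ(1.1/SE)]. The last two columns are for an unadjusted t-test on scores.

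| SD of MMSE scores | SE, 30 per arm | Chance of a gap above 1.1 | Power for 1.1 points, 25 per arm | n per arm for 80% (normal formula) |
|---|---|---|---|---|
| 1.3 (plan) | 0.336 | 0.1% | 83% | 22 |
| 2 | 0.516 | 3.3% | 48% | 52 |
| 3 | 0.775 | 16% | 25% | 117 |
| 4 | 1.033 | 29% | 16% | 208 |
| 5 | 1.291 | 39% | 12% | 325 |

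The chance passes 5% at an SD of 1.1 / (1.96 × 0.258) = 2.2.

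**What stratification does.** Take a normal severity model, a two-level split at the median and a CDR–MMSE correlation of 0.8 (all assumed). Stratifying removes 0.8² × 2/π = 41% of the MMSE variance from the between-arm difference. At SD 5 the SE falls from 1.291 to 1.291 × √0.59 = 0.99, and the chance of a gap above 1.1 falls from 39% to 27%. At a correlation of 0.7 the share removed is 31%. A 20/80 split at a correlation of 0.8 also removes 31%.

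**Why the analysis must follow the assignment.** After stratification the estimate varies less, but an unadjusted t-test still computes its standard error from the full spread. The test becomes conservative and, when scores vary widely, loses power.

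**What baseline adjustment does.** The residual SD is SD × √(1 − r²), where r is the correlation between baseline and endpoint (assumed).

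- SD 3, r = 0.9: 3 × √0.19 = 1.31, needing 23 per arm.
- SD 3, r = 0.7: 3 × √0.51 = 2.14, needing 60 per arm.
- SD 5, r = 0.9: 5 × √0.19 = 2.18, needing 62 per arm.

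Adjustment recovers much of the loss, but it does not rescue 25 per arm in every case.

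**The case against.** Broad entry is a legitimate choice, and the documents do not describe how severe the recruited patients will be. Consent by a legal tutor is no evidence of severe disease, because WP2 allows it too and WP2 also recruits MCI patients. This stands: severe patients may be randomised, but nothing shows that they will be.

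The 1.3 may be an SD of change. At a score SD of 3 and a correlation of 0.9, the SD of change is 3 × √(2 × 0.1) = 1.34, close to the plan's figure. A t-test on change would also cancel most of a baseline gap. Task 3.6 does not exclude this reading, but it does not state it either, so it is a reason to clarify the plan and not a defence of it.

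The plan foresees patients who "fail in neuropsychological assessment, fecal collection or treatment adherence", and answers with 5 to 10 extra patients per group. That helps with numbers. It does nothing for balance or for the spread of scores.

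A reader might infer that chance imbalance biases the comparison or inflates the type I error. It does neither under randomisation.

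A reader might also infer that patients at the floor or ceiling of the scale cannot show an effect, and compute a diluted one. A floor blocks measured decline, not gain; a ceiling still lets slower decline be seen. Patients who cannot be tested give missing data, which is a different problem. The documents give no share of such patients, so no power loss can be put on it.

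**Conclusion.** The point holds in a limited form. Entry is open to any severity, severity plays no part in the assignment, the named test is unadjusted, and the meaning of the planning SD is not stated. At an assumed score SD of 3 to 5, arms of 30 would differ at baseline by more than 1.1 MMSE points in 16% to 39% of randomisations. At 1.3 the figure is 0.1%, so the size of the problem depends on a spread the documents do not give. The cost is in precision and interpretability, not validity.

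Two further inferences are not supported. One is that the trial needs an MMSE entry window: that is a trade-off against recruitment and generalisability, and nothing in the documents fixes its limits. The other is that stratifying by CDR would remove most of the imbalance: under the assumptions above, a median split removes about 41% of the variance.

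**What to change.** **Task 3.1:** stratify the assignment by baseline CDR at two pre-specified levels, with balance enforced within each stratum (for example, by blocks). Make the assignment after the Task 3.2 tests and before product is handed over.

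**Task 3.6:** compare the arms on MMSE with a model that includes treatment, the CDR stratum and baseline MMSE, in place of the unadjusted t-test. The two changes belong together, because stratifying while keeping the unadjusted test can lower power.

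**Sample-size paragraph:** state whether 1.3 is the SD of scores or of change, and confirm that it suits the analysis chosen.

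**Cost:** protocol wording, a two-stratum list, and CDR scored during the visit so that the stratum is known before handover. Both scales are already collected, so there is no new test or visit and no narrowing of the population.

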Volunteers were contacted and cited for an interview (at the same hospital, center Alzheimer's Association or at home, the more comfortable to them). In order to obtain the stool sample, the researcher will explain the instructions (a paper with the written instructions will be with the kit too) and encourage to collect 1-2 days before the interview and keep in the freeze until they deliver us in the interview (stool collection and preservation system, Norgen, Biotek Corporation, Canada).

At the time of the interview, the volunteer will come accompanied and give the stool sample in the saving tube of the collection kit.

The assessment will include:

-Patient identification, sex, age, level of education, years of schooling, weight and height and diagnostic (others sociodemographic data) and revision of the inclusion/exclusion criteria

-Medication, diseases (diabetes, cholesterol, hypertension, etc)

-Tests/scales:

-Mediterranean lifestyle index interview (MEDLIFE), (Sotos-Prieto, et al, 2015), MEDLIFE will give us information about how the patient follow Mediterranean diet and habits;

-Live Events Questionnaire-Cuestionario de sucesos vitales (CSV), (Sandín & Chorot, 2017), CSV the information about successful stress events that could affect and modify the main relations of the study

-Screening cognitive tests/scales: Mini Mental State Examination (MMSE) (Folstein et al, 1975), Global Deterioration Scale-Functional Assessment Staging (GDS-FAST) (Reisberg, 1982, 1988), Clinical Dementia Rating (CDR) (Hughes, 1982)

-Cognitive Reserve scale (León-Estrada et al, 2017)

-Activities of Daily Living (ADLs) and Neuropsychiatric scale (Test Barcelona-2), (Peña-Casanova, 2019)

-Anxiety and Depression Scale (Goldberg et al 1988)

-Test Barcelona-2 battery, beta abbreviated version (Peña-Casanova, 2019), we will use Test Barcelona-2 battery to an extensive and deep neuropsychology assessment.

The patients were requested not to change their ordinary physical activity and not to take any nutritional supplements during the 12-week trial. The researcher will give to the volunteer in this meeting the treatment to take from the day after the interview until 12 weeks after and a new stool collection kit (in order to bring another stool sample, the next interview day, after 12 weeks).

Task 3.3. Citation of the volunteers after the probiotic intake period: assessment and stool sample collection

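### WP3 recruits from hospitals and a stimulation centre, but neither recruitment source nor dementia medication is used in the randomisation or the MMSE comparison: a cheap gain in precision is missed

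*Combined protocol and SAP*

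**What the plan says.** All references are to WP3 of the combined protocol and SAP.

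- **Sources (Task 3.1).** Patients are approached in the hospitals by neurologists and neuropsychologists, and also by neuropsychologists of the Alzheimer's Association. On the Association's centre the plan says: "In the Alzheimer stimulation center of Alzheimer Association come regularly about 60-70 patients". The share of the 60 trial patients expected from it is not given.
- **Eligibility (Task 3.1).** Inclusion rests on a neurology diagnosis of AD and age over 65. The exclusions name several drug classes and probiotics, but not dementia medication or stimulation.
- **Allocation (Task 3.1).** "30 will ingest the probiotic mixture and 30 will ingest placebo (randomized assignment to the groups will be done"). No strata, blocks or minimisation factors are named.
- **Sample size (Task 3.1).** "We used 1.3 as SD and 1.1 as the difference in mean (d) of MMSE as key variable". From this the plan derives 25 evaluable patients per arm, and an allowance of 5 losses per arm brings the target to 30.
- **Data (Tasks 3.2 and 3.3).** The baseline list contains "Medication, diseases (diabetes, cholesterol, hypertension, etc"), and the same assessment is repeated at 12 and 24 weeks. Recruitment source and centre attendance are not on the list. Patients are asked to hold physical activity constant and to avoid supplements; nothing comparable is said about dementia medication or stimulation.
- **Analysis (Task 3.6).** Assessment results are compared between groups by Student's t-test and Pearson chi-square, so a score such as MMSE falls to the t-test. The one multivariable model relates microbiota to neuropsychological results and names no covariates.

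**The concern.** MMSE is the key variable, and two background factors may plausibly bear on it: attending a stimulation centre and taking dementia medication. The trial may mix patients who differ on both. The centre's regular attenders are about as many as the whole trial, so a substantial centre share is possible.

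Two practical consequences follow if either factor is related to MMSE. Its contribution stays in the error term of an unadjusted t-test, which widens the confidence interval. And with 25 to 30 patients per arm, the baseline table could show a noticeable difference in source or medication. A reader could then question the result, with no pre-specified adjusted analysis to answer them. For source, the data to make the adjustment later might not exist.

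**Working it through.** **1. The plan's own figure.** Inputs from Task 3.1: difference 1.1, SD 1.3, alpha 0.05 (taken as two-sided, since sidedness is not stated), power 80%.

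- Normal approximation: n = 2 × [1.3 × (1.960 + 0.842) / 1.1]² = 21.9, so 22 per group.
- t-distribution version, matching the planned test: 22.9, so 23 per group.
- The stated 25 is close to this and slightly conservative. At 25 per group the t-test has 83% power. Adding 5 dropouts gives 30.

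The sample size stands on its own inputs and is not disputed here.

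**2. Chance imbalance.** Assumption, not in the documents: 30 of the 60 patients come from the centre. Under an unstratified 30:30 allocation, the number of centre patients in one arm is hypergeometric (60 patients, 30 from the centre, 30 drawn).

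- P(18 v 12 or worse, either direction) = 0.196.
- P(18 or more in the probiotic arm specifically) = 0.196 / 2 = 0.098.
- If the factor is held by 30% or 70% of patients, the chance of a difference of 20 percentage points or more is 0.158.

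A 20-point difference in a factor worth g MMSE points shifts the observed treatment difference by 0.2 × g. For g = 1 that is 0.2 points, or 0.2 / 1.1 = 18% of the planned effect.

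**3. Precision.** Assumption: one binary factor held by half the patients, with an MMSE effect of g points. Its variance is 0.5 × 0.5 × g². There are two cases, and the documents do not settle which applies.

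*Case A: the factor's variance lies outside the SD of 1.3 and is left in the error.* Total SD = √(1.3² + 0.25 g²).

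| g (points) | Total SD | Power at 25 per group | n per group for 80% |
|---|---|---|---|
| 0.5 | 1.32 | 82% | 24 |
| 1.0 | 1.39 | 78% | 27 |
| 1.5 | 1.50 | 72% | 31 |
| 2.0 | 1.64 | 64% | 36 |

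Adjusting for the factor would bring the residual SD back to 1.3 and power back to 83%.

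*Case B: the 1.3 is already the total SD.* There is no loss against the plan. For g = 1 the residual SD after adjustment is √(1.69 − 0.25) = 1.20, and power at 25 per group rises from 83% to about 89%.

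**4. Steps 2 and 3 are not separate harms.** In Case A the squared standard error of the treatment difference is 2(1.69)/25 + 2(0.25 g²)/25. The second term is the chance-imbalance variance. For g = 1 it is 0.02, an SD of √0.02 = 0.14 points. It is already inside the SD of 1.39 that gives 78% power, so the two must not be added.

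**The case against.** The strongest reply has four parts.

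- **Randomisation already deals with this.** It balances both factors in expectation, and the t-test's standard error includes their variation, so type I error is preserved. This stands. A reader might infer that the mixed sources bias the treatment effect; the documents do not support that.
- **The size rests on assumed inputs.** The centre's share, the effect on MMSE and its relation to the SD of 1.3 are nowhere in the documents. The SD is taken from a previous trial whose sample may already have mixed background treatments. This also stands. The 64% figure needs a 2-point effect, nearly twice the 1.1 targeted for the probiotic, wholly outside the planned SD, so it should not be the headline.
- **The mechanism is partly inferred.** A reader might suppose that hospital patients join just as their medication is started or changed, or that centre patients will show a fresh response to stimulation. Nothing says so. The criteria are silent on dementia medication for both sources, the sources may overlap, and what the centre's stimulation consists of is not described. Regular attendance suggests an established activity rather than a new one.
- **The plan has partial safeguards.** Descriptives of all collected data by group would show a medication imbalance. Task 3.1 also allows for 5 to 10 further patients per group against losses; with 30 evaluable per group, power at SD 1.39 would be 85%. A methodology specialist may add analyses. These help only in part: a specialist consulted at the analysis stage cannot stratify in retrospect, recover attendance that was not recorded, or make an adjustment pre-specified.

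**Conclusion.** The point holds as a cheap improvement in precision and credibility. The plan draws on two sources, states no strata, collects medication without using it in the MMSE comparison, and does not list centre attendance.

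On the assumption of a 1-point factor held by half the patients, the stake is about 5 percentage points of power either way: 78% instead of 83% if the factor lies outside the planned SD, or 83% instead of about 89% if it lies inside. On the assumption that half the patients come from the centre, there is also about a one-in-five chance of an 18 v 12 or worse split by source. If neither factor is related to MMSE, the gain is nil and the cost is close to nil.

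The sample size of 25 evaluable and 30 recruited per group is unaffected. The documents do not support a claim of systematic bias or of a trial that is underpowered against its own assumptions.

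**What to change.** **Task 3.1.** Stratify the randomisation by recruitment source (stimulation centre v hospital) in permuted blocks. State how a patient known to both sources is classified.

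**Task 3.2.** Add recruitment source and centre attendance to the baseline form.

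**Task 3.6.** Replace the unadjusted MMSE t-test with a pre-specified ANCOVA of follow-up MMSE on treatment arm, baseline MMSE, recruitment source and baseline dementia-medication use (yes/no). The yes/no split can be read from the medication item already collected. A finer level for recently started or changed medication could not, because that item lists no start or change dates. Adjust for baseline values only. Report medication starts and changes at weeks 12 and 24 by arm, keeping all patients in the main comparison.

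**Cost.** A two-stratum list, one form line and about three degrees of freedom (with 50 evaluable patients, 48 falls to 45, which changes power at SD 1.3 by about 0.1 percentage point). No extra visits or patients, and no change to any patient's treatment. The strata and the form line must be in place before enrolment. Whether to set any eligibility rule on medication is a clinical decision for the sponsor and is not proposed here.

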Alignment with hospitals' procedures: All the protocols will be presented to the hospitals and decide if there is any aspect that does not fit with the hospitals procedure and align to them, in order to fit the procedure protocol with all the procedures of the hospitals involved.

Task 1.2. Final protocol presentation to the Ethical Committee of Clinical Research with Medicines (CEICm)

Apply for CEICm authorization: The project will be written in a specific template and presented to the Ethical Committee of Clinical Research with Medicines (CEICm) of the Institut d'Investigació Sanitària Pere Virgili (IISPV), since it is the Ethical Committee of reference to our center. When authorization is available, the study will be able to begin.

Risks and solutions envisaged for task 1.2: Risk: negative resolution. Contingency: modify the aspects that they pointed to not accept the project and apply again. This can delay us one or two months at most and we still were on time to achieve the objectives and the project. In this sense we have already dealt with similar situations requesting the approval of the aforementioned committee, with always reaching a positive resolution.

Task 1.3. Publicity of the study to enroll participants

Publicity of the study will be done (flyers, posters, etc.) and will be disseminated in all the hospitals involved. All the neuropsychologist and neurologist of the participant hospitals will have the study information and the informed consent (for the first study) ready to give to the target patients.

WP2.- Dementias and microbiota

To evaluate the relationship between dementias and their features with microbiota composition it is important to make a deep assessment of these features and control possible influencing variables as Mediterranean diet and lifestyle adherence, stressful events and cognitive reserve. A deep interview about medication and other illnesses will be conducted. Individual and sociodemographic data will be also collected.

The general objective of WP2 is to study the microbiota composition of the most known dementias: Alzheimer Disease (AD), Parkinson Disease Dementia (PDD), Lewy Bodies Dementia (LBD), Frontotemporal Dementia (FTD)-behavioral variant, comparing them to healthy control subjects in relation to their neuropsychological, neuropsychiatric and functional state.

The following tasks will be carried out in this WP:

Task 2.1. Patients recruitment

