There will be two assessments after 12-week treatment period and 24-week treatment period. At the time of the interview, the volunteer will come accompanied and give the stool sample in the saving tube of the collection kit. The assessment will be the same that in task 3.2.

The researcher will give to the volunteer in the 12-week meeting the treatment to take from the day after the interview until 12 weeks after and a new stool collection kit (in order to bring another stool sample, the next interview day, after 12 weeks).

Task 3.4. Stool samples saving

Same as task 2.4.

Task 3.5. Stool samples shipment to laboratory analysis

Same as task 2.5.

Task 3.6. Obtainment of the data and statistical analysis

The fecal samples will be analyzed by Sequencing Technics and characterize their bacterial taxonomic composition. These data will be received within 2-3 months after the samples reach the analyzer laboratory.

Statistical analysis with microbiota data and all other data collected will be done. All the descriptive for all the data collected will be calculated for each group. Microbiota data from experimental groups and the results of the assessments will be compared (Student's t-test and Pearson Chi-square test). Multivariable logistic regression analyses will be done to relate microbiota composition and results of the neuropsychological assessment.

At the moment of statistical analysis will be ask a methodology specialist to revise them and decide if any other analysis could be interesting to do.

Risks and solutions envisaged for task 3.6: Risk: data loss. Contingency: In order to ensure no data loss, a periodical back-up will be carried out.

WP 4.- Dissemination and formation

This WP aims to effectively disseminate our results in international conferences, publishing the results in international scientific journals of high impact factor (1Q-2Q) and disseminate to the benefit society directly as well as educate of the benefits of the variables studied and resulted positive, e.g. the Mediterranean lifestyle, probiotic consumption etc. To achieve this objective, the following tasks will be carried out in this WP:

Task 4.1. Attendance and presentation of communications to congresses

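### WP3 asks patients to keep physical activity unchanged and avoid supplements but says nothing on diet, and its microbiota comparison names no use of the diet measure it collects, leaving avoidable noise in the gut-composition result

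*Combined protocol and SAP*

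**What the plan says.** All places are in the combined protocol and SAP.

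- **Request to patients (WP3, Task 3.2):** "The patients were requested not to change their ordinary physical activity and not to take any nutritional supplements", for a trial that the same sentence describes as lasting 12 weeks. No other part of WP3 asks patients to keep their usual diet.
- **Treatment period (Task 3.1):** "The duration of the treatment will be 24 weeks, with two posttreatment assessment, at 12 weeks and at 24 weeks".
- **Diet as an influencing variable (WP2 rationale):** the plan regards it as important to "control possible influencing variables as Mediterranean diet and lifestyle adherence, stressful events and cognitive reserve".
- **Diet as a measurement in WP3 (Tasks 3.2 and 3.3):** at baseline, "MEDLIFE will give us information about how the patient follow Mediterranean diet and habits". For the visits at 12 and 24 weeks, "The assessment will be the same that in task 3.2", so MEDLIFE is taken three times.
- **Objective (WP3 introduction):** to learn about "potential positive probiotic effects in the gut composition and on their clinical symptoms".
- **Analysis (Task 3.6):** descriptive statistics by group for everything collected; t-tests and chi-square tests to compare microbiota and assessment results between arms; and logistic regression relating microbiota to the neuropsychological results. No diet covariate is named in any of these. A methodology specialist may propose further analyses when the data are analysed.

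**The concern.** Gut composition is one of the two things WP3 sets out to change, and diet is a factor the plan itself lists as able to influence the relations under study. The request to patients fixes physical activity and excludes supplements, yet leaves diet free. A patient could change diet substantially over the treatment period without departing from anything asked.

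Randomisation balances diet at entry on average. It does not remove the spread in diet between patients, and it does not prevent diet from changing afterwards. In an unadjusted comparison both sources sit in the residual variance. At stake is the precision of the gut-composition result in a trial planned around 25 evaluable patients per arm.

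**Working it through.** **1. The plan's own figure, and whether it depends on this point.** Task 3.1 gives SD 1.3, difference 1.1 on the MMSE, alpha 0.05 and power 80%, and arrives at 25 per arm. It does not say whether the test is one- or two-sided; I take two-sided.

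- Normal formula: n = 2 × [1.3 × (1.960 + 0.842) / 1.1]² = 21.9, so 22 per arm.
- Exact t-test: 22.9, so 23 per arm.
- The stated 25 is slightly generous: power at 25 is 84.9% (normal) or 83.4% (t-test). Adding 5 dropouts gives 30.

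The calculation concerns the MMSE only. No microbiota variance or effect enters it, so the diet point does not alter it, and it gives no power for a microbiota outcome.

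**2. Where diet enters the microbiota comparison.**

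| Step | Activity | Supplements | Diet |
|---|---|---|---|
| Request to patients (Task 3.2) | keep unchanged | do not take | not mentioned |
| Measured at 0, 12 and 24 weeks (Tasks 3.2, 3.3) | – | – | MEDLIFE |
| Named in the microbiota comparison (Task 3.6) | no | no | no |

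The measurement exists. What is missing is the request and a stated use of the measurement in the comparison.

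**3. What noise from diet does.** Let R be the share of the outcome's total variance that comes from diet. Without that share the variance would be (1 − R) times as large. The unadjusted comparison therefore has a standard error 1/√(1 − R) times larger and needs 1/(1 − R) times as many patients for equal precision. The documents give no value of R; the values below are assumptions.

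| R (assumed) | Standard error × | Patients × |
|---|---|---|
| 5% | 1.026 | 1.05 |
| 10% | 1.054 | 1.11 |
| 20% | 1.118 | 1.25 |
| 30% | 1.195 | 1.43 |

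This is the most that perfect control of diet could recover. A request and a lifestyle index will recover only part of it.

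**4. What a baseline covariate costs and gains.** With 25 per arm the unadjusted comparison has 50 − 2 = 48 residual degrees of freedom. If baseline MEDLIFE has within-arm correlation ρ with the outcome, the variance of the adjusted difference is on average (1 − ρ²) × [1 + 1/(48 − 2)] = (1 − ρ²) × 1.022 times the unadjusted one.

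- If MEDLIFE explains nothing, the standard error rises by √1.022 − 1, about 1%.
- The model breaks even at ρ² = 1 − 46/47 = 1/47, about 2%. Above that it gains precision.

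**5. Which remedy addresses which part.** The covariate removes noise from diet differences present at entry. It does not remove later change. The request is aimed at later change. The two are complementary.

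**The case against.** The strongest reply is that leaving diet free while measuring it repeatedly is a defensible design for a randomised placebo trial, and that the comparison of arms stays valid without any diet instruction. That stands: the issue is precision, not validity.

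The words about controlling influencing variables are also in the rationale for WP2, an observational comparison of diagnostic groups. WP2 gives its participants no diet instruction and simply measures diet, so the plan is not contradicting itself. That stands too. But WP3 uses the same instrument and the same kind of outcome, so the reason for attending to diet carries over.

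A further reply is that the methodology specialist could add an adjustment later. That is possible, but a covariate chosen once the data are in hand is weaker than one fixed in advance.

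Three stronger readings are tempting, and the documents do not support them.

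- **That MEDLIFE goes unused.** Task 3.6 promises descriptive statistics by group for all data and compares assessment results between arms, which covers MEDLIFE. The gap is narrower: no use is named in the microbiota comparison.
- **That the result is biased between arms.** With randomisation and a placebo, diet drift is alike in both arms on average. A difference requires that allocation becomes known; WP3 states no masking, but that is a separate matter. A product effect on eating would arguably be part of the treatment effect. Nothing shows that the MEDLIFE interview itself prompts patients to change diet.
- **That power falls by a stated amount.** Starting from 80% at 25 per arm, adding 10% or 30% to the variance gives about 76% or 69%. The arithmetic is correct, but the added variances are invented and the plan claims no power for a microbiota outcome.

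**Conclusion.** The point holds in a limited form. WP3 neither asks patients to keep their usual diet nor names the diet measure it collects in the microbiota comparison, so some avoidable noise remains in the gut-composition result. The direction is clear, on the plan's own premise that diet may influence the relations studied. The size cannot be derived from the documents and could be negligible; the range in the working rests wholly on assumed variance shares. Arm-related bias is conditional on allocation becoming known and is not established. The MMSE comparison and its sample size do not depend on this point. It is a modest improvement, worth making because it needs no new data.

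**What to change.** 1. **Task 3.2:** add ordinary diet to the existing request and have it apply to the whole treatment period. The request speaks of a trial of 12 weeks while Task 3.1 sets treatment at 24 weeks; these passages must be reconciled.
2. **Task 3.6, microbiota comparison:** replace the unadjusted t-test with a linear model (ANCOVA) containing arm and baseline MEDLIFE.
3. **Task 3.6, summaries:** name MEDLIFE change by arm at weeks 12 and 24 within the by-group descriptives already planned.
4. **Task 3.6, sensitivity analysis:** use on-study MEDLIFE only here. It is measured after randomisation, so adjusting the main comparison for it could remove part of a treatment effect.

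The cost is a slightly longer request to patients and one more covariate, worth about 1% in standard error if MEDLIFE proves uninformative. MEDLIFE is a broad lifestyle index and may miss short-term changes, so the sensitivity analysis should be read with that limit in mind. If patients have already been enrolled under the present request, items 2 to 4 can still be fixed before the data are analysed.
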